Surgical Technique: The donor area of the palate is located between the root of the canine and the palatal root of the first molar. Its lateral border is positioned approximately 2 mm from the gingival margin and its medial border is dictated by the position of the palatal neurovascular bundle which can be found 7, 12, or 17 mm from the cemento-enamel junction of the correspondent teeth, depending on whether the palatal vault is shallow, average, or high, respectively. A single horizontal incision, whose length corresponds to the required length of the graft, is made at 90° to the underlying bone approximately 2 mm from the gingival margin with a #15 blade. The blade is then angled at approximately 135° to the bone and a split-thickness dissection is started within that first incision, towards the median of the palate. As the incision is advanced, the angle of the scalpel is further flattened until it is nearly parallel to the bone surface. Elevation of the overlying tissue should be avoided to reduce the risk of perforation while making this incision. Split-thickness dissection continues until the necessary dimensions of the graft are obtained, ideally maintaining 1.0-1.5 mm of overlying tissue. The SECTG is separated from the surrounding tissue via incisions to the bone surface at the mesial, distal, and medial borders of the graft. The graft is detached from the bone with a periosteal elevator and placed on a saline-soaked gauze until it is transferred to the recipient site.

The length, width, and thickness of the graft, the thickness of the remaining palatal tissue, and the length of the palatal incision will be measured with digital calipers to the nearest 0.1 mm. Palatal incisions will be closed with cyanoacrylate. Immediately following completion of the

surgical procedure, Group A will receive PBM treatment of the donor site with Er:YAG laser according to the parameters shown to induce maximal proliferation of human gingival fibroblasts (Energy Setting: 80 mJ, Pulse Rate: 25 Hz, Duration: 30 s). Group B will receive sham treatment with the laser unit turned off.

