During all sessions of laser treatment, the manufacturer-recommended safety precautions will be stringently adhered to. The clinician, patient, and any other individuals inside the operatory must always wear Laser Safety Glasses designated for use with Er:YAG lasers. Whenever possible, the individuals present within the operatory will be limited to the patient and those directly involved with the procedure (i.e. the clinician and assistant). The activated laser should never be directed anywhere other than the intended site of treatment. If the operator, patient, or anyone else in the operatory suspects they may have incurred damage to their eyes or skin, they should be examined by a dermatologist and/or ophthalmologist. A sign of notification that laser surgery is in progress will be placed at the entrance of the operatory. The Er:YAG laser is not intended for use on patients who have a pacemaker or implantable cardioverter defibrillator, however these patients would not fit the inclusion criteria of ASA I and ASA II classification and thus would already be precluded from participation in the study. The laser unit should not be used in the presence of combustible anesthetic or an elevated concentration of oxygen. If the administration of oxygen is absolutely necessary, it will be ensured that there is no leakage of oxygen and the oxygen delivery tube will be protected with a non-combustible cuff.

Both groups will receive 2 g of Amoxicillin (or 600 mg of Clindamycin in cases of penicillin allergy) and 400 mg of Ibuprofen immediately following surgery, in addition to the standard post-operative instructions given to patients at the U of M Graduate Periodontics Clinic. This includes

application of an ice pack for the first 24 hours, BID rinsing with 0.12% Chlorhexidine, avoiding the surgical sites during oral hygiene, avoiding hot foods and liquids, avoiding hard and crunchy foods for 24 hours after surgery, refraining from smoking for two weeks and avoiding sucking on straws or spitting. Patients will also be provided with a bag of 30 200-mg Ibuprofen tablets. They will be given a Visual Analogue Scale (VAS) questionnaire to rate their post-operative pain from 0 to 10 for each night of the first post-operative week.

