All data will be recorded based on the subject's assigned number after they have agreed to participate and have signed the consent form. Their names and contact information will be stored in a secure, locked location at the U of M Graduate Periodontics Clinic. Findings from the

study may be published or presented in a public forum. Participants' names will not be used and no identifying details revealed.

STATISTICAL ANALYSIS PLAN

The study will be blinded at the level of data collection and data assessment. The primary outcome for this study is the patients' post-operative discomfort from the palatal donor site during the first week following surgery. This is assessed by VAS scores and analgesic consumption. Friedman's two-way ANOVA test will compare the change in VAS scores over time within each treatment group. Mann-Whitney U test will compare the difference in VAS scores between the two groups at each time point as well as the differences in total analgesic use between the two groups. The secondary outcomes are healing of the donor site and the palatal wound's effect on the patients' OHQoL. Healing is assessed by MEHI and HI scores and by tissue thickness. Wilcoxon Signed Ranks test will compare the change in MEHI and HI scores from week one to week two within each treatment group. Mann-Whitney U test will compare the differences in MEHI and HI scores between the treatment groups as well as the differences in tissue thickness at six weeks post-operatively between the groups. OHQoL is assessed by OIDP scores. The differences in OIDP scores between treatment groups is compared with Mann-Whitney U test. The level of significance is $p \leq 0.05$. IBM SPSS Statistics for Windows (Version 25.0) is used for analysis.

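### The primary outcome is discomfort over the first week, but VAS is compared between arms only night by night, unadjusted, with no lead night and no week-level comparison

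*Combined protocol and SAP*

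**What the plan says.** The STATISTICAL ANALYSIS PLAN section defines the primary outcome as patients' post-operative "discomfort from the palatal donor site during the first week following surgery". Two measures assess it: VAS scores and analgesic consumption. Under Clinical Methodology, patients "rate their post-operative pain from 0 to 10 for each night of the first post-operative week". The number of ratings is not printed; I read it as seven.

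Two analyses of VAS are planned:

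- Within arms, Friedman's "two-way ANOVA test will compare the change in VAS scores over time within each treatment group".
- Between arms, "Mann-Whitney U test will compare the difference in VAS scores between the two groups at each time point".

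For analgesics, the Mann-Whitney test compares "the differences in total analgesic use between the two groups". One significance level, p ≤ 0.05, is given for everything. The section names no lead night, no multiplicity adjustment, and no mean, area under the curve or longitudinal model for VAS.

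Healing has the same two layers. Within arms, "Wilcoxon Signed Ranks test will compare the change in MEHI and HI scores from week one to week two within each treatment group". Between arms, "Mann-Whitney U test will compare the differences in MEHI and HI scores between the treatment groups". Tissue thickness and OIDP are also compared between arms.

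**The concern.** The primary question concerns a week, but for VAS the plan answers it in seven separate pieces. If one night is significant and the others are not, nothing in the SAP says whether the laser reduced discomfort over the week. The choice of night is left to the author or reader. Seven unadjusted tests also raise the chance that some night is significant when the laser does nothing.

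The two measures of one outcome are treated inconsistently, because analgesic use does get a single week-level comparison. The Friedman test cannot fill the gap for VAS: it asks whether pain changes across nights inside one arm and says nothing about laser against sham. The plan therefore produces no week-level VAS difference between arms, which is the quantity a pilot would most usefully pass on to later research.

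**Working it through.** The documents give no sample size, power, effect size or SD, so there is no stated figure to reproduce. The counts below come from the SAP. Everything simulated rests on assumed inputs.

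**1. Count of VAS and within-arm tests.** Between-arm VAS tests: 7, if there is one per night. Week-level between-arm VAS tests: 0. Within-arm tests: 1 Friedman × 2 arms + 2 healing indices × 2 arms = 6.

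**2. False positives if nights were independent.** 1 − 0.95^7 = 0.302.

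**3. False positives with correlated nights.** Nights within a patient are correlated, so the true figure is lower. Two models were simulated, each with 4,000 replicates, 10, 15 and 20 patients per arm, no effect, and a Mann-Whitney test per night.

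*Model A.* Whole-number scores 0-10, patient SD 1.6, night-to-night error SD 1.3 with autocorrelation 0.5, mean pain falling linearly over the week (4.0 to 1.4, 5 to 1, or 3 to 1). Before rounding, the correlation of adjacent nights is (1.6² + 0.5 × 1.3²) / (1.6² + 1.3²) = 3.405 / 4.25 = 0.80. At least one night was significant in 18.1-19.5% of trials, and the weekly mean in 4.5-5.4%. Repeats with fresh draws widen these to about 16-20% and 3-5%.

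Varying the adjacent-night correlation (curve 4.0 to 1.4):

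| Correlation | n = 10 | n = 15 | n = 20 |
|---|---|---|---|
| 0.96 | 11.5% | 12.1% | 12.5% |
| 0.91 | 14.2% | 13.5% | 15.4% |
| 0.64 | 22.7% | 24.4% | 23.3% |
| 0.50 | 27.0% | 26.0% | 26.9% |
| 0.33 | 27.3% | 28.7% | 26.5% |

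The weekly-mean test stayed at 4.1-5.4% throughout.

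*Model B.* Normal scores, every pair of nights equally correlated:

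| Correlation | n = 10 | n = 15 | n = 20 |
|---|---|---|---|
| 0.3 | 24.5% | 25.1% | 26.8% |
| 0.5 | 20.9% | 21.8% | 23.4% |
| 0.7 | 17.5% | 16.6% | 19.1% |
| 0.9 | 10.9% | 10.2% | 12.2% |

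Weekly mean: 4.2-5.0%. Across both models the nightly range is about 10-29%.

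**4. What a weekly mean costs in power.** Model A, with three benefits that each average 1 point over the week; for the fading one, (2 + 2 + 1.5 + 1 + 0.5 + 0 + 0) / 7 = 1. The comparator is any night significant after Holm adjustment, whose false-positive rate with no effect was 2.5-2.8% (curve 4.0 to 1.4).

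| Benefit | Weekly mean | Holm, any night |
|---|---|---|
| Constant 1 point | 20-40% | 11-27% |
| Fading | 22-44% | 25-67% |
| Late (fading reversed) | 13-31% | 22-62% |

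Each range spans the assumed arm sizes, which is why the columns overlap.

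**5. Precision.** With no effect, the Hodges-Lehmann 95% interval for the weekly-mean difference had median width 3.1, 2.6 and 2.1 points at 10, 15 and 20 per arm.

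**6. The second primary measure.** With one VAS test and one analgesic test, the chance of any false positive is 1 − 0.95² = 0.0975 if independent. With seven nightly tests plus analgesics it is 1 − 0.95^8 = 0.337 if all are independent.

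**The case against.** A reader might infer something stronger: that the trial will judge the laser by change within each arm, or does not compare the arms at all. The documents do not support this. The SAP compares the arms by Mann-Whitney on VAS, analgesic use, MEHI, HI, tissue thickness and OIDP. It nowhere says that the six within-arm p-values will be contrasted or used as evidence for the laser. Within-arm tests are acceptable as description. Calculating how often one arm alone would be significant prices a contrast the plan does not propose, and for healing it would need score scales that the documents do not give. That part reduces to a labelling note.

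Four further objections have weight:

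- **This is a pilot.** Strict error control matters less there. But the plan names a primary outcome and a significance level, and a week-level estimate with an interval suits a pilot better than seven p-values.
- **The weekly mean is not uniformly better.** In the simulations it beats Holm-adjusted nightly tests for a constant benefit and loses for both time-limited ones. Holm alone would answer the false-positive complaint, though without a single estimate for the week. This stands, so the choice should follow the expected shape of the benefit.
- **One VAS test does not make one primary test.** Analgesic use remains. This also stands.
- **It may be too late to prespecify.** The document is dated October 16, 2020, after the stated recruitment period of Fall 2018 to Spring 2020. It does not say whether the arm codes were open.

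**Conclusion.** The point holds for VAS. The missing lead, adjusted or week-level between-arm VAS analysis is plain from the SAP and depends on no assumption beyond reading the schedule as seven nights. Its size does depend on assumptions: with 10 to 20 per arm and no effect, about 16-20% of trials show at least one significant night in the base case, against about 3-5% for one weekly-mean test. Two-sided testing is also assumed, since the SAP does not state it.

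This should be changed because the repair is cheap and the plan as written gives a less clear answer to its own primary question. It does not invalidate the trial: the arms are compared on every outcome, and the data needed are already collected.

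**What to change.** Add to the SAP:

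1. **Lead VAS analysis.** Name one between-arm comparison for the week, for example Mann-Whitney on each patient's mean (or area under the curve) over the nights, with the Hodges-Lehmann difference and its 95% interval. State how missed nights are handled.
2. **Nightly tests.** Keep them and label them supportive and unadjusted. If a time-limited benefit is expected, Holm-adjusted nightly tests are an acceptable alternative lead.
3. **Timing.** Make the choice before the arm codes are opened. If they are already open, report the week-level analysis as post hoc.
4. **The two primary measures.** Name VAS or total analgesic use as lead, or adjust across the two. Otherwise, state that the chance of any primary false positive is about 10% if they are independent.
5. **Labelling note.** State that the Friedman and Wilcoxon within-arm tests are descriptive and that treatment conclusions rest on the between-arm tests.

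The cost is a few SAP lines, one derived variable, and one test with its interval, using the same data and software. The real price is the loss of power for a benefit confined to part of the week, early or late, if the weekly mean is chosen.

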At the one-week post-operative appointment, the participants will return their VAS questionnaires and any remaining Ibuprofen tablets. They will be asked to fill out a modified Oral Impacts on Daily Performance (OIDP) questionnaire to assess the effect of the palatal wound on their oral-health related quality of life during the first post-operative week. A clinician who did not perform the surgery and is blinded to which treatment group the patient belongs will assess the donor site at the one- and two-week post-operative appointments according to a modified early-wound healing index (MEHI) proposed by Fickl (a variation of the EHI originally conceived by Wachtel) as well as the healing index (HI) of Landry, Turnbull and Howley. Participants will return for a six-week post-operative appointment, during which tissue thickness at the donor site will be measured via bone sounding and a histological specimen will be harvested with a tissue punch. Tissue samples will immediately be submerged in a solution of 10% neutral buffered formalin. Clinical photographs will be taken at all appointments.

Risks

There is the risk in both the test and control groups of post-operative complications that are associated with any periodontal surgery including intraoral pain or discomfort, bleeding,

infection, swelling and bruising. There is also a risk that the desired outcome, either partial or complete root coverage (depending on the severity and classification of the initial recession defect), may not be achieved by the surgical procedure.

Potential Benefits

If Er:YAG photobiomodulation of the palatal donor site results in improved and/or faster healing of the tissue or less post-operative discomfort, then patients requiring SETGs will benefit from a shorter and more pleasant healing period following their surgery. Also, as the effects of Er:YAG PBM on healing have never been investigated in human studies, the information gained from this study would help direct future research on this topic.

Consent Process

Patients of the Graduate Periodontics Clinic at the University of Manitoba who require SECTG and who meet the eligibility requirements will be asked personally if they would like to be a part of the project. After being given a brief description of the research, if the patient is interested, they will be provided a written summary of the study and a consent form to sign if they would like to take part.

Data Security

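### The primary outcome is tested eight times between the arms at p ≤ 0.05, with no lead test, adjustment or success rule and no whole-week VAS comparison of the arms

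*Combined protocol and SAP*

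**What the plan says.** The Statistical Analysis Plan names a single primary outcome, discomfort at the palatal donor site in the week after surgery. Of its measurement it says: "This is assessed by VAS scores and analgesic consumption". Neither measure is ranked above the other.

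Three analyses serve this outcome:

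- **VAS between arms:** "Mann-Whitney U test will compare the difference in VAS scores between the two groups at each time point".
- **Analgesic use between arms:** the same sentence continues "as well as the differences in total analgesic use between the two groups".
- **VAS over time:** Friedman's "two-way ANOVA test will compare the change in VAS scores over time within each treatment group".

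The data behind them are described under Clinical Methodology. Patients "rate their post-operative pain from 0 to 10 for each night of the first post-operative week". They are also "provided with a bag of 30 200-mg Ibuprofen tablets", and at one week "the participants will return their VAS questionnaires and any remaining Ibuprofen tablets", so analgesic use is a single whole-week total.

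The significance level is p ≤ 0.05 throughout. The documents contain no multiplicity adjustment, testing order, lead time point or statement of what counts as a positive primary result. They give no sample size.

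**The concern.** The outcome is defined over a week, but the VAS comparison between arms is split into separate nights. Friedman's test does not fill the gap: it asks whether pain changes over time inside one arm, and a significant result in one arm but not in the other is not a treatment comparison.

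The plan does not say whether one significant night is enough, whether analgesic use must agree, or how opposite results on the two measures would be read. That choice can then be made after the results are seen, and the error rate depends on it.

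The study is a pilot, and Potential Benefits says its information "would help direct future research on this topic". The practical risk is that a chance result favouring the laser is carried forward as a positive primary finding.

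**Working it through.** The plan gives no error rate or power figure to reproduce, so the check counts the tests and then works out the error rate under each rule a reader might apply.

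**Count (from the documents).** One rating per night for one week gives 7 VAS tests; the number seven is inferred, not printed. Total analgesic use adds 1. Total: 7 + 1 = 8, each at 0.05.

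**Any-one-of-eight rule, no further assumptions on the data.**

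- If the tests were independent: 1 − 0.95^8 = 0.337 (the seven VAS tests alone: 1 − 0.95^7 = 0.302).
- Upper bound under any dependence: 8 × 0.05 = 0.40.
- If one further rating were taken, for example surgery night counted separately: 1 − 0.95^9 = 0.370.

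**Allowing for correlation.** Nightly scores in the same patient are correlated, so 33.7% is only a reference value. A null simulation (264 scenarios, 10,000 replicates each) used these inputs, none of which is in the documents:

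- 10, 20 or 30 patients per arm.
- VAS means falling from 4 to 1 or from 3 to 0.2 over the seven nights, SD 2, then rounded and clipped to 0-10.
- Tablets with mean 12 and SD 6, rounded and clipped to 0-30.
- Nightly correlation 0.3-0.95 (exchangeable) or 0.7-0.95 (autoregressive).
- VAS-analgesic correlation 0.2-0.9, omitting infeasible combinations.
- Tie-corrected two-sided Mann-Whitney tests, without continuity correction at all sizes and also with it at 10 per arm.

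| Rule for a positive primary result | False-positive rate |
|---|---|
| Any one of eight, either direction | 11.2-31.2% |
| Any one of eight, favouring the laser | 5.4-16.0% |
| At least one night and analgesic use | 0.5-4.9% |
| Holm over mean VAS and analgesic use | 2.4-5.2% |
| Holm over all eight | 1.2-4.5% |
| One test on the seven-night mean VAS | 4.2-5.5% |

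A single two-sided 5% test favours the laser by chance 2.5% of the time, which is the comparison for the second row.

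The low end of the first row comes from the strongest VAS-analgesic correlation: 11.2-15.4% at 0.9, against 13.8-31.2% at 0.2. A separate simulation with untied normal scores, 10, 15 or 30 per arm, nightly correlation 0.3-0.9 and VAS-analgesic correlation 0.3-0.5, gave 16-33% for any one of eight.

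**Opposite directions.** With the positive VAS-analgesic correlations above, both measures are significant in opposite directions under the two-test Holm in fewer than 0.1% of null trials. If patients who take more ibuprofen report less pain, the correlation could be negative. At −0.4 the figure is about 0.4-1.1%.

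**The case against.** The strongest reply is that this is a pilot. The plan fixes the level of each test and makes no explicit claim of success, so what is undefined is the family-wise rate, and that matters only if some combination of tests is read as success. On this view family-wise control is a matter of judgement, and one sentence calling the tests exploratory would be enough. That sentence would indeed be an acceptable repair, but the plan does not contain it. It names a primary outcome and a threshold, and that invites a verdict.

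A second reply is that the simulated figures rest on outside inputs. This is true. Only the count of eight, 33.7% under independence and the 40% bound need no assumed sample size, spread or correlation. Even so, at nightly correlations up to 0.95 the any-one rate stays above twice the nominal 5%.

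A third is that the laser is applied straight after surgery, so benefit may be confined to the first nights, and a weekly mean would dilute it. This stands as a real cost, and it is why Holm over all eight tests is kept as an alternative. A weekly mean also needs a rule for missed nightly ratings.

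Finally, the document is dated October 16, 2020, after the planned Spring 2020 end of the participant window. Whether the data had been unblinded is not stated. If they had, no new primary test can count as prespecified.

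**Conclusion.** The concern holds and should be fixed. The eight tests, the single threshold, and the absence of a lead test, adjustment or success rule follow directly from the text. So does the lack of a whole-week VAS comparison between arms; analgesic use does have one.

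The plan does not have a 33.7% error rate. It has no defined error rate for its primary result: the rate is several times 5% under one plausible reading and at or below 5% under another. The sizes rest on the assumed sample sizes, distributions and positive correlations listed in the check. The defect itself does not depend on them. Pilot status lowers the weight of the point but does not remove it.

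**What to change.** Amend the Statistical Analysis Plan as follows.

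1. Replace the seven nightly primary tests with one Mann-Whitney test on each patient's seven-night mean (or area under the curve) VAS, and state how missed ratings are handled.
2. Keep total analgesic use as an equal primary measure. Apply Holm across the two: the smaller p-value against 0.05/2 = 0.025, then the other against 0.05.
3. Report the seven nightly differences descriptively, with Hodges-Lehmann estimates and 95% confidence intervals.
4. Show both primary estimates side by side, and state that significant results in opposite directions are inconclusive.

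If benefit is expected mainly in the first nights, keep all eight tests under Holm instead (first step 0.05/8 = 0.00625). If no confirmatory claim is intended, label all eight p-values exploratory. If the data are already unblinded, label the choice post hoc and report all eight results.

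The cost is wording only, with no new data, but an isolated significant night would no longer count as a positive primary result. Simulated power (6,000 replicates, 10 or 20 per arm, nightly correlation 0.5 or 0.7, VAS-analgesic correlation 0.35, all assumed):

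| Assumed benefit | Relevant measure alone at 0.05 | Same measure in two-test Holm | Holm over eight |
|---|---|---|---|
| 2 VAS points, nights 1-2 only | mean VAS 10-24% | 5-16% | 26-73% |
| 1 VAS point every night | mean VAS 20-50% | 12-39% | 11-34% |
| 6 fewer tablets, no VAS effect | tablets 51-85% | 37-77% | 16-57% |

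The Holm-over-eight column is any significant test in the first two rows and the tablet test in the third. For the early-only benefit, any unadjusted test favouring the laser would be significant about 66-94% of the time under the present plan, but at the inflated error rate. Testing VAS first in a fixed sequence is not proposed: in the tablet-only case it would leave 2-4% power for the tablet test.

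### Every comparison rests on a rank test at p ≤ 0.05, and this pilot pre-specifies no effect estimate, confidence interval or variability summary

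*Combined protocol and SAP*

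**What the plan says.** The Statistical Analysis Plan is a single paragraph. Its primary outcome is donor-site discomfort in the first week: "This is assessed by VAS scores and analgesic consumption". Under Clinical Methodology, patients "rate their post-operative pain from 0 to 10 for each night of the first post-operative week", which gives about seven time points.

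The planned analyses are:

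- **VAS within arm:** "Friedman's two-way ANOVA test will compare the change in VAS scores over time within each treatment group".
- **VAS between arms:** "Mann-Whitney U test will compare the difference in VAS scores between the two groups at each time point".
- **Analgesics between arms:** the same test, "as well as the differences in total analgesic use between the two groups".
- **Healing indices within arm:** "Wilcoxon Signed Ranks test will compare the change in MEHI and HI scores from week one to week two within each treatment group".
- **Healing indices between arms:** "Mann-Whitney U test will compare the differences in MEHI and HI scores between the treatment groups", with the same test for six-week tissue thickness.
- **OIDP between arms:** Mann-Whitney.

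The only decision rule is a significance level of 0.05. The paragraph names no effect measure, interval or descriptive summary. No sample size, power or precision target appears in the document, and recruitment is bounded only by a calendar window.

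The title labels the study a pilot. Potential Benefits, after the benefit to patients, says that "the information gained from this study would help direct future research on this topic".

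**The concern.** Whoever plans the next trial needs a plausible effect size, its uncertainty and the spread of the outcome. A p-value supplies none of these, and the plan commits to nothing else.

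In a small study the distinction affects the conclusion. A p-value above 0.05 can come from an interval centred near zero or from one that reaches well into large benefit, and the planned output does not separate the two.

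Testing VAS night by night makes this worse. The primary outcome covers the whole week, but no single quantity represents it. The plan would give about seven separate verdicts on VAS and one on analgesic use. Estimates could be computed afterwards, but the choice of nights, summary and estimator would then be made with the data in view.

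**Working it through.** **1. Is any estimate planned?** The plan has no figure of its own to reproduce, so the first check is a reading of the text.

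| Outcome | Within-arm test | Between-arm test | Estimate, CI or SD/IQR planned |
|---|---|---|---|
| VAS, each night | Friedman | Mann-Whitney at each time point | None |
| Total analgesic use | – | Mann-Whitney | None |
| MEHI, HI | Wilcoxon signed-rank | Mann-Whitney | None |
| Six-week thickness | – | Mann-Whitney | None |
| OIDP | – | Mann-Whitney | None |

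The paragraph is complete, with no sign of redaction or lost text at this point.

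**2. How wide would an interval be?** The inputs are the two-sided 95% level (matching the stated 0.05, with two-sidedness assumed), equal arms (the ratio is not stated) and n per arm. The documents give no n, so 10 to 20 is assumed.

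Half-width in SD units = t(0.975, 2n−2) × √(2/n)

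- n = 10: 2.101 × 0.447 = 0.94
- n = 15: 2.048 × 0.365 = 0.75
- n = 20: 2.024 × 0.316 = 0.64

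Multiplying by an assumed SD of 1.5 to 3 on the 0–10 VAS gives 1.41 to 2.82 points at n = 10 and 0.96 to 1.92 points at n = 20.

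**3. What could a non-significant comparison hide?** Suppose the observed difference is 0.3 SD in favour of the laser.

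- n = 10: 0.3 ± 0.94, or −0.64 to 1.24 SD
- n = 20: 0.3 ± 0.64, or −0.34 to 0.94 SD

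Both intervals include zero, so neither result is significant, and both also include 0.8 SD. With an observed difference of exactly zero, the interval still reaches 0.94 SD at n = 10 and 0.64 SD at n = 20.

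**4. Does the t interval stand in fairly for a rank-based one?** Hodges-Lehmann intervals were simulated for rounded 0–10 scores with an assumed SD of 2. Their mean half-widths were about 1.9, 1.5 and 1.3 points at n = 10, 15 and 20. The t formula with SD 2 gives 1.88, 1.50 and 1.28. The two agree closely.

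**5. How often would the plan give a significant result?** A single Mann-Whitney test on normal data with a true 0.5 SD benefit has simulated power of about 0.16, 0.24 and 0.32 at n = 10, 15 and 20. That is one test. The plan tests about seven nights. With the same 0.5 SD shift every night and an assumed between-night correlation of 0.8 or 0.5, the chance that at least one night reaches p ≤ 0.05 runs from about 0.37 (n = 10, correlation 0.8) to 0.74 (n = 20, correlation 0.5). Single-test power therefore does not describe what the whole plan would yield, and the conclusion below does not use it.

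**The case against.** Three stronger readings are tempting, and the documents support none of them.

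- **That informing later research is the study's stated purpose.** The sentence stands under Potential Benefits, after the benefit to patients. No section states an objective, and nothing says that the study will size a later trial. The named primary outcome is comparative discomfort, which the planned tests do address.
- **That the study cannot supply such information.** The plan is silent on estimates but does not exclude them. Nightly VAS, returned tablets, index scores, OIDP and thickness are collected per patient, so estimates and spreads can be derived. The gap is in what is pre-specified.
- **That the trial would probably end non-significant and be misread as showing no effect.** No sample size is given, and step 5 shows that across seven nights at least one significant result may be likelier than not. Nor does the plan say how p > 0.05 will be interpreted.

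It can also be said that a missing sample size is a separate matter, since adding an interval does not raise power. That is correct. The half-widths here show only how much a bare p-value leaves unsaid.

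Lastly, one Hodges-Lehmann shift for every outcome would suit coarse ordinal indices with many ties poorly, and a weekly VAS summary is a new measure, so the change goes beyond wording. Both points stand, and the fix allows for them.

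The objection does not remove the omission itself. Estimates chosen after the data are seen are weaker than pre-specified ones, and the plan at present names none.

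**Conclusion.** The concern holds as an omission in the analysis plan. Every comparison is a rank test at 0.05, VAS is tested separately at each time point, and no effect estimate, confidence interval or variability summary is pre-specified. The planned results would therefore not show how large or how uncertain any effect is, in a pilot said to help guide later work.

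With an assumed 10 to 20 per arm, the 95% half-width for a mean difference is about 0.94 to 0.64 SD, so one non-significant comparison could still be compatible with a large benefit. That figure also assumes equal arms and roughly normal means. It shows the scale of the problem and does not predict this trial's result.

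The change is worth making because it alters what a small study can conclude and needs only data already collected.

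**What to change.** Amend the Statistical Analysis Plan as follows:

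1. Define a one-week VAS summary per patient, for example the mean of the nightly scores. The night-by-night comparisons can stay as description.
2. For that summary, total analgesic use, OIDP and six-week thickness, make the between-group difference with its 95% CI the main result. Name the estimator in advance (Hodges-Lehmann or mean difference).
3. For MEHI and HI, which are ordinal, show the score distributions by arm with a rank-based effect measure and its CI, for example the probability that a patient in one arm scores better than a patient in the other.
4. Report SD or IQR by arm for each outcome.
5. Keep the Mann-Whitney p-values as secondary.

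The cost is one added VAS summary measure and a little more output. No new data or visits are needed.
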